## 1. Change Control

Updated SAP version no.	Section number changed	Description of change	Date changed

### 4. List of abbreviation and definitions of terms

Abbreviation	
ASD	Absolute standard difference
CCP-UK	Clinical Characterisation Protocol UK
CO-CIN	Covid-19 Clinical Information Network
CONSORT	Consolidated Standards of Reporting Trials
CRF	Case report form
DCMO	Deputy chief medical officer
EAMS	Early Access to Medicine Scheme
ECMO	Extracorporeal membrane oxygenation
GCP	Good clinical practice
ISARIC 4C	Coronavirus Clinical Characterisation Consortium
NICE	National Institute for Health and Care Excellence
RDV	Remdesivir
SAP	Statistical analysis plan
SpO 2	Oxygen saturation
WHO	World Health Organisation

## 5. Statement of Compliance

This Statistical Analysis Plan (SAP) provides a detailed and comprehensive description of the pre-planned final analyses for the study. Version 1.0 was agreed prior to seeing any data. It is written using the template ST001TEM01, and incorporating recommendations for the writing of SAPs for observational studies made by Hiemstra *et al*. These analyses will be performed by the study statistician.

All analyses are performed with standard statistical software (SAS v9.4 or later, and R v3.6 or later). The finalised analysis datasets, programs and outputs will be archived following Good Clinical Practice (GCP) guidelines and SOP GE012 Archiving procedures. The testing and validation of the statistical analysis programs will be performed following SOP ST001.

## 6. Background and Rationale

In the current COVID-19 pandemic, therapeutic treatments are being sought, in particular in the care of severe disease. Several therapeutic drugs licensed for use in the treatment of other conditions have been trialled in the treatment of COVID-19. One drug of key interest in the UK setting, is Remdesivir (RDV). This was made available on 26th May 2020 in the UK under the MHRA EAMS (Early Access to Medicine Scheme), and on 3rd July it was moved from EAMS status to being clinically commissioned, based on the evidence available at the time. An assessment of efficacy of RDV in the UK is now sought.

### 6.1. EAMS Background

The MHRA EAMS (Early Access to Medicine Scheme) is a form of compassionate use programme. EAMS aims to give patients with life threatening or seriously debilitating conditions access to medicines that do not yet have a marketing authorisation when there is a clear unmet medical need. The scheme is voluntary and operates within the current regulatory structure. The MHRA requires that a Registry be utilised to support capture of the real-world outcomes of the use of an EAMS medicine in UK patients. Data captured through an EAMS are expected to be used to support cost effectiveness and commissioning discussions as the medicine is licensed and becomes available for routine clinical use in the UK.

The Deputy Chief Medical Officer (DCMO) for Her Majesty's Government has mandated that data on all patients that receive Remdesivir through the EAMS must be captured through the ISARIC 4C Clinical Characterisation Protocol UK (CCP-UK) case report forms (CRFs), as coordinated by the COVID-19 Clinical Information Network (CO-CIN). Completion of the mandatory fields of the ISARIC WHO CCP-UK CRFs is required, to support ongoing implementation, including determination of future drug allocations between NHS hospitals, and evaluation ([link to forms](#)).

The DCMO has commissioned an analysis of efficacy and safety based on the pragmatic data being collected by CO-CIN.

#### 6.1.1. Remdesivir EAMS

Gilead Sciences has submitted RDV to the EAMS scheme as a treatment for hospitalised patients with severe COVID-19.

### 6.1.2. Post July 2020

EAMS status of RDV was withdrawn in July 2020, and it was clinically commissioned for use in the UK. This was following an evidence review by the National Institute for Health and Care Excellence (NICE). The data collection initiated to evaluate RDV under EAMS has continued.

### 6.2. Clinical trial evidence

At the time of writing, results from two key clinical trials (ACTT-1, and SOLIDARITY) have been published/publicised. The ACTT-1 trial was carried out between February 21 to April 19, 2020 – giving early evidence for RDV compared with placebo. SOLIDARITY ran from March 22 to October 4, 2020, which included a comparison of RDV with ‘local standard of care’. These suggest that for patients that are hospitalised with COVID-19, who require additional oxygen, but who do not initially require ventilation: RDV is effective compared with placebo in (a) reducing time-to-recovery; (b) improving clinical status at 15 days; (c) improving 28-day mortality; but RDV is not effective compared with ‘standard of care’ in (d) reducing time-to-recovery; (e) improving 28-day mortality. Over time, standard of care has evolved, and this may in part explain the lack of the benefits of RDV observed in SOLIDARITY. Both trials reported no benefit of RDV for patients that were more seriously ill at baseline: those initially requiring ventilation.

## 7. Study objectives

This documents proposed an ‘ideal-case’ analysis to address the objectives below. As data are observational, it is accepted some aspects of data quality and sample size may make some parts of what is proposed infeasible. The analysis may need to be adapted, in the light of the data, but a record of all changes together with rationales will be documented in the Change Control (Section 1 above).

### 7.1. Primary Objective

Evaluation of the efficacy of RDV in reducing 14-day mortality in newly diagnosed, hospitalised, non-ventilated severe COVID-19 patients.

### 7.2. Secondary Objectives

Evaluation of the efficacy of RDV in improving other key outcomes such as speed of recovery, hospital stay, and clinical status over the 28-days post diagnosis in newly diagnosed, hospitalised, non-ventilated severe COVID-19 patients.

## 8. Study design

### 8.1. Overall study design

This is a prospective, observational non-interventional matched cohort study, within the ISARIC 4C CCP, of hospitalised patients with severe COVID-19. Patients treated with RDV will be compared with matched controls (or if this is infeasible, with all patients satisfying key inclusion/exclusion criteria – see below). The time-scale is from baseline to 28 days post baseline.

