##### 8.4.2. Exclusion criteria

- Requiring a high flow cannula, any ventilation or ECMO during first 24 hours post baselinec
- Pregnant
- Chronic kidney disease
- RDV initiated  $> 24$  hours post baselined
- Is a COVID-19 re-admission (was previously hospitalised for COVID-19)
- Missing Day 1 Daily Treatment CRF
- Missing ‘Medication’ section of the Outcome CRF

---

a RDV was recommended in people aged 12 and over, and weighing over 40kg. Weight was not generally measured at baseline for practical reasons, so we have excluded children aged 12-17 in order to be sure that no-one in the control group was likely to weigh less than 40kg.

b This criteria is an ideal, to measure the effectiveness of RDV initiated close to baseline. If RDV is more routinely given later than this, we will either remove this criteria, or move the window of inclusion to say 3 days. Statistics describing when RDV treatment was initiated compared with baseline, will be presented.

c This subgroup will be analysed separately (see Section 19).

d See footnote b above.

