### 8.7. Definition of treatment groups

The analysis cohort will be split into two treatment groups: RDV and non-RDV. As the study is observational, allocation of treatment is decided by clinicians.

A matching process will be carried out to link RDV patients with non-RDV patients as follows:

A logistic regression with dependent variable RDV (Yes/No) will be fitted including the following covariates:

1. Month of baseline
2. Tier of participating centre (0 / 1 and 2)
3. Sex
4. Age
5. Broad ethnicity group (White / Asian / Black / Other)
6. Clinically extremely vulnerable status (Yes: Cancer / Yes: Severe respiratory condition / Yes: on immunosuppression therapy / Yes: Other / No)
7. Comorbidities: Diabetes (Y/N), Hypertension (Y/N), Obesity (Y/N), Chronic Cardiac disease (Y/N), CPD (Y/N), Asthma (Y/N)
8. Where COVID was acquired (Community / Hospital)
9. Admitted to HDU/ICU at baseline (Y/N)

Note: a pragmatic approach will be taken – the list above defines a best-case set of matching criteria; it may be necessary for categories to be collapsed to simplified discriminators (e.g. White vs Other ethnicity, or ‘Total number of comorbidities’), should the model become over-parametrised. If possible, 2nd order interactions will be investigated, and if statistically significant, added to the model. All main effects will be retained in the model, even if not significant.

The fitted model will be used to calculate the probability of receiving RDV for each patient according to their baseline factors. The probability calculated is called their propensity score (PS). Boxplots will

be presented showing the distribution of PS in each treatment group. Patients who were given RDV will then be matched to a control patient / patients with a similar PS who did not get RDV, using a nearest neighbour matching algorithm and a pre-specified maximum difference in PS (calliper width) of 0.2 standard deviations. The ratio of RDV patients to controls may be 1:1 or higher – to a maximum of 1:4 (Rassen (2012) suggests that 1:n matching leads to higher precision in estimating effect sizes, with a cost of a small increase in bias with increasing n). Controls are chosen without replacement, so may not be matched to more than one RDV patient.

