The matched cohort will be checked for balance, by using the disease risk score diagnostic described by Stuart (2013): an underlying primary outcome risk score will be calculated using the following analysis dataset: all non-RDV patients satisfying inclusion/exclusion. The primary outcome will be modelled using logistic regression, and the following key risk factors will be fitted as covariates: sex, age, and number of comorbidities. (These are chosen from Knight 2020^9, and as being the most measurable for most members of the cohort.) The fitted model will be used to calculate a primary outcome risk score (RS) for each patient included in the matched cohort. The mean and SD of RS will be calculated for each treatment group. The groups will be checked for balance by calculating the absolute standardised difference in RS:

$$ASD_{RS} = \frac{|\overline{RS}_T - \overline{RS}_C|}{\sqrt{\frac{s_T^2}{2} + \frac{s_C^2}{2}}}$$

Where  $s_T$  and  $s_C$  are the standard deviation of RS in RDV and control groups respectively.

If  $ASD_{RS} < 0.1$ , the matching will be considered balanced.

If matching is found to have been unsuccessful in balancing treatment and control groups, the propensity score model will be revised.

Patients from either treatment group that are not matched will be excluded from inferential analyses, and will be described separately.

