## 17.2. Analysis of Outcomes

### 17.2.1. Primary Outcome

The percentage of patients that died by the end of day 14 will be presented for each group. Risk of death will be modelled using logistic regressionf,10, with treatment group fitted as a covariate, and ideally adjusting for the key confounders: age, sex, and number of comorbidities at baseline. The odds-ratio comparing RDV with controls, estimated from the model, will be presented together with a 95% CI and a p-value.

Note on adjustment for confounders: the number of covariates that may be added to the model depends on the number of deaths recorded (rule of thumb, 10 events per covariate fitted). Clinical trials data indicate that 14-day mortality for RDV in this type of patient may be around 3.1%, meaning that if we include 500 RDV-treated patients, we might expect 16 deaths from that group. Under the assumption that the risk of death is not lower in the control group, this suggests at least 32 deaths (under 1:1 matching), and so we project that there will be sufficient power to enable adjustment for 3 confounders given the higher expected matching ratio.

---

f Stuart (2010) recommends that in the analysis of cohorts matched using propensity scoring, it is more common to simply pool all the matches into matched treated and control groups and run analyses using the groups as a whole, rather than using the individual matched pairs.

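### If matching is judged infeasible, the primary 14-day mortality comparison falls back to all eligible patients, with no trigger and no model that keeps six of the matching covariates

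*SAP*

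**What the plan says.** - **Comparison (SAP 8.1).** RDV patients are compared with matched controls, "or if this is infeasible, with all patients satisfying key inclusion/exclusion criteria". The forward reference there leads to the eligibility criteria and the matching section; neither says when matching counts as infeasible.
- **Matching (8.7).** The propensity score (PS) model includes "Month of baseline", "Tier of participating centre (0 / 1 and 2"), ethnicity, clinically extremely vulnerable status, place of acquisition and HDU/ICU admission, besides sex, age and individual comorbidities. The section calls this a best-case list. If balance fails, the PS model is revised. "Patients from either treatment group that are not matched will be excluded from inferential analyses".
- **Primary model (17.2.1).** Logistic regression on treatment, "and ideally adjusting for the key confounders: age, sex, and number of comorbidities at baseline". No other model is given for an unmatched comparison.
- **Adaptation (section 7).** "The analysis may need to be adapted, in the light of the data", with changes and reasons to be logged in Change Control.

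**The concern.** Under matching, the PS carries most of the confounder control and the outcome model only tidies up. Section 8.1 allows the matching to be dropped without saying what replaces it. If the analyst then applies the only outcome model on the page, control shrinks to three covariates at most.

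Calendar time is the clearest loss. Section 8.2 says that standard of care evolved and that corticosteroids became recommended for some patients part-way through. Section 13.2 intends to cover both waves, and section 8.4 states no calendar start for controls. If RDV use and background mortality both moved over those months, an unmatched odds ratio mixes the drug with the period. At stake is the study's main result: an inert drug could appear to help or to harm.

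Because infeasible is undefined and no step puts the decision before outcomes are seen, a reader of the final report could not tell whether the switch rested on baseline data alone.

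**Working it through.** **1. The plan's own figure.** Section 17.2.1 expects 16 deaths among 500 RDV patients at 3.1%, and at least 32 in total at 1:1. 500 × 0.031 = 15.5, rounded up to 16; doubled, 31 to 32. Both reproduce. At 1:1 that is 31/3 = 10.3 deaths per confounder, or 31/4 = 7.75 if treatment is counted too.

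**2. Which factors are covered where.**

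| Factor | PS model (8.7) | Outcome model (17.2.1) | Risk score for balance check (8.7) |
|---|---|---|---|
| Age, sex | yes | ideally | yes |
| Comorbidities | individually | ideally, as a count | as a count |
| Month of baseline | yes | no | no |
| Centre tier | yes | no | no |
| Ethnicity | yes | no | no |
| Vulnerability | yes | no | no |
| Place of acquisition | yes | no | no |
| HDU/ICU admission | yes | no | no |

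Six factors are controlled only through the PS. The balance check cannot be relied on to show imbalance in them, so it is also a poor guide to whether matching has worked.

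**3. Illustration with calendar time omitted.** All inputs are assumed; the SAP gives none of them. Two periods of equal size, no drug effect, 14-day mortality 12% then 6%.

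- RDV use 10% then 50%: 
 RDV risk = (0.1 × 0.12 + 0.5 × 0.06)/0.6 = 0.0700 
 control risk = (0.9 × 0.12 + 0.5 × 0.06)/1.4 = 0.0986 
 OR = (0.0700/0.9300)/(0.0986/0.9014) = **0.69**
- RDV use 50% then 10%: 
 RDV risk = (0.5 × 0.12 + 0.1 × 0.06)/0.6 = 0.1100 
 control risk = (0.5 × 0.12 + 0.9 × 0.06)/1.4 = 0.0814 
 OR = (0.1100/0.8900)/(0.0814/0.9186) = **1.39**

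**4. A wider range.** Take one omitted binary factor, a true OR of 1 and an RDV-group risk of 3.1% (17.2.1). The other inputs are assumed: the factor multiplies the odds of death by 1.5 to 3, and its prevalence is 20% in one group against 40% to 60% in the other. If it is commoner in controls, the spurious OR runs from 0.92 to 0.64; if commoner in RDV patients, from 1.09 to 1.57. With 500 RDV patients and 2,000 to 5,000 controls, a two-sided 5% test then rejects in about 6% to 40% of studies.

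**5. Could the six factors simply be added to the outcome model?** They need about 16 parameters: month 6 (assuming May to November), tier 1, ethnicity 3, vulnerability 4, acquisition 1, HDU/ICU 1. With treatment and the three stated covariates this makes 20. By the plan's rule of 10 deaths per covariate that is 200 deaths, or 200/0.031 ≈ 6,450 patients at 3.1%. The matched design expects 31 (1:1) to about 78 (1:4: 2,500 × 0.031 = 77.5). Direct adjustment therefore needs a large control pool; a PS method does not spend events in this way.

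**6. Does PS weighting remove the bias in step 3?** Weight each control by e/(1 − e), where e is the probability of RDV, and each RDV patient by 1. With use of 10% then 50%, control weights are 1/9 and 1. Weighted control risk = (0.9 × 1/9 × 0.12 + 0.5 × 1 × 0.06)/(0.1 + 0.5) = 0.042/0.6 = 0.0700, equal to the RDV risk, so OR = 1. With use reversed, 0.066/0.6 = 0.1100 and again OR = 1.

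**The case against.** The best defence is that section 8.1 says who is compared in the fallback, not how they are modelled. Section 8.7 calculates a PS for each patient, and nothing forbids using it without matching. That stands: the fallback is unspecified rather than prescribed in a faulty form, and the loss of control arises by omission. But 17.2.1 is the only model written, so it is what a programmer following the SAP would run.

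Safeguards also exist. Section 5 says version 1.0 was agreed before any data were seen, section 7 requires changes to be logged with reasons, matching is clearly preferred, and section 11 concedes the limits of observational data. These make a switch visible. They do not set its trigger or its timing.

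Three stronger readings are tempting, and the SAP does not support them.

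- A reader might infer that the open RDV window ("we will either remove this criteria, or move the window of inclusion to say 3 days"), the open ratio ("The ratio of RDV patients to controls may be 1:1 or higher") and the word ideally multiply into a menu from which the best odds ratio can be picked. They are conditional choices: the window depends on when RDV was routinely started, the ratio on the supply of controls, and the adjustment on the number of deaths. Section 17.2.1 itself projects that all three confounders can be included. An error rate that assumes free selection does not describe this plan.
- A reader might infer that the risk-score check exposes the treatment effect while the PS model can still be revised. It fits the outcome in non-RDV patients only and compares predicted risks, so it shows no treatment contrast.
- A reader might infer that 8.1 and 8.7 flatly contradict each other over unmatched patients. The exclusion in 8.7 can be read as belonging to the matched route; a cross-reference would settle it.

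**Conclusion.** The concern holds in a limited form. The primary comparison may change to all eligible patients on an undefined condition, and the only stated model would then leave six of the plan's own matching covariates uncontrolled, including calendar time, over which the plan says care evolved. This should be corrected before the analysis is run.

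The size and direction of the bias are not known. The SAP gives no RDV uptake by month, no mortality trend and no covariate prevalences. The odds ratios of 0.69 and 1.39 rest on assumed inputs and show only that the bias could be material and could fall on either side of 1. It would be wrong to infer that the fallback favours RDV. If matching goes ahead, the bias described here does not arise.

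**What to change.** 1. In 8.1 and 17.2.1, state the fallback model: the section 8.7 PS in the full eligible cohort, weighted to the RDV-treated population so that the target agrees with the matched analysis, with robust standard errors and the three 17.2.1 covariates. If overlap weights are used instead, state that the target population changes.
2. Define infeasible from baseline data only, for example by the share of RDV patients matched within the calliper and by balance on each 8.7 factor. Record the decision before outcomes in RDV patients are examined.
3. Delete the word ideally in 17.2.1, so that three-covariate adjustment is the default.
4. State in 8.7 that the exclusion of unmatched patients applies to the matched analysis only.

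Cost: SAP wording, one weighted analysis if the fallback is used, and somewhat lower precision than a crude comparison. No new data are needed. Two limits remain. If matching fails because the groups overlap poorly, some control weights will be large and their distribution should be reported. Weighting also does not cure missing covariates: section 18 already allows a shorter list, and any factor dropped should be named.

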### 8.2. Treatments studied

The key treatment of interest is RDV, given to patients at the early stage of a COVID-19 infection who have a high probability of developing severe disease. Guidelines were in place for its use in the UK – it was recommended for newly hospitalised patients, no later than within 10 days of symptom onset, and only initiated in non-ventilated patients. Patients were recommended to receive 200mg on Day 1 of treatment, followed by 100mg daily for 4 days. An optional additional 5 days of 100mg daily was recommended till 29th September, but the wording changed over time:

26th May to 2nd June: “If a patient does not demonstrate clinical improvement”

3rd June to 28th September: “If a patient deteriorates and progresses to ventilation and/or ECMO treatment”

29th September onwards: “Ensure that clinicians prescribe a maximum treatment course of 5 days” – this was due to a disruption in supply of the drug. It is stated that some exceptions may receive additional doses, but these were undefined by the guidelines.

The comparison treatment is: Standard of care, without RDV.

NB: Standard of care evolved as knowledge of the disease and how to treat it evolved. Co-medication with the corticosteroids dexamethasone and hydrocortisone became recommended for some patients part-way through our study period – these are not expected to interact with RDV, and so we expect that RDV patients will have received these in the same way as non-RDV patients. The drugs Hydroxychloroquine and Chloroquine phosphate were not recommended as concomitant medications for RDV from 3rd September 2020.

### 8.3. Baseline: definition

We take a common baseline to be ‘date of hospitalisation due to COVID’. It is important to note that this is not necessarily when RDV was initiated, though it is likely that it was administered soon after admission. The definition of baseline depends on the where the infection was acquired:

Community acquired COVID-19 i.e. admitted with symptoms consistent with COVID-19:

Baseline = Date of admission to hospital

For hospital acquired COVID-19 :

Baseline = Date positive COVID-19 test was collected

‘Hospital acquired’ is defined as: symptom onset at least 5 days after hospital admission.

#### 8.4. Patient population studied

Inclusion/exclusion guidelines for RDV use changed slightly over time. The following criteria are designed to create a cohort of patients that would have been eligible to receive RDV from baseline. They apply for the whole study period, and will be used to define our analysis cohort:

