##### 8.4.1. Inclusion criteria

- Laboratory confirmed SARS-CoV-2 infection
- Hospitalised
- Aged  $\geq 18$  yearsa at baseline
- Requiring supplementary oxygen ( $SpO_2 \leq 94\%$ ) at any time during 24 hours post baseline
- RDV initiated  $\leq 24$  hours post baseline (RDV group only)b

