## 17. Efficacy Evaluations

### 17.1. Demographics and other baseline characteristics

Descriptive statistics will be used to describe demographics and other baseline characteristics, including pre-existing comorbidities for (a) the full analysis cohort, (b) the matched cohort, split by treatment group.

Categorical data will be summarised by numbers and percentages. Counts for missing values will be also tabulated but missing values will not be considered in the percentages. Continuous data will be summarised by mean, standard deviation, median, lower quartile, upper quartile, minimum and maximum. Variables to be included are as follows:

- Gender (Male/Female)
- Age, reported as a continuous variable (years) and also by age-group (18-30, ..., 71-80, 81+)
- Broad ethnicity (White / Black / Asian / Other)

- Non-white ethnic origins (Arab/Black/East Asian/South Asian/West Asian/Latin American/Aboriginal/First Nations/Other)
- Clinically extremely vulnerable status (None / Cancer / Severe respiratory condition / Immunosuppression therapy / Other)
- Comorbidities (Diabetes, Hypertension, Obesity, Chronic Cardiac disease, CPD, Asthma, Other)
- Where COVID was acquired (Community / Hospital)
- Number of days since onset of symptoms
- Admitted to HDU/ICU

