### 17.2.2.3. Time-to-death

We restrict this analysis to deaths within 28 days of baseline. Any patient alive at the end of the study period will be censored at 28 days. Any patient lost to follow-up prior to 28 days will be censored at their last known follow-up. This outcome will be analysed as a time-to-event using the methodology described in 17.2.2.1 above.

### 17.2.2.4. Clinical status at day 15

Clinical status is defined as an 8-point ordinal score with the following categories: (1) Not hospitalised, and not limited physically; (2) Not hospitalised, but limited physically and/or requiring supplementary oxygen; (3) Hospitalised but medically OK; (4) Hospitalised, not requiring supplementary oxygen, but needs on-going COVID related care; (5) Hospitalised and requiring supplementary oxygen; (6) Hospitalised and requiring non-invasive ventilation; (7) Hospitalised and requiring mechanical ventilation or ECMO; (8) Dead. See Appendix A1.1 below for a definition of how this outcome is derived. Where day 15 CRFs are unavailable, we will look at all available adjacent CRFs to estimate a

---

g We have used the same definition for this outcome as was used in the ACTT-1 trial.

most likely clinical status. In cases where there is ambiguity over likely clinical status, and independent statistical reviewer, blind to all but the clinical status CRF data, will adjudicate likely status. If it is not possible to estimate the outcome, the outcome will be treated as missing.

The outcome will be analysed using a proportional odds model with treatment arm and disease severity as covariates, and adjusting for key confounders: age, sex, and number of comorbidities at baseline. The treatment odds ratio estimated from the model will be presented along with a 95% CI and a p-value.

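### Symptom duration and graded oxygen need are left out of the cohort definition or the matching, and the only balance rule cannot register imbalance in either

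*SAP*

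**What the plan says.** - **Eligibility.** SAP 8.4 describes its criteria thus: "The following criteria are designed to create a cohort of patients that would have been eligible to receive RDV from baseline". SAP 8.2 reports that guidelines recommended RDV "no later than within 10 days of symptom onset, and only initiated in non-ventilated patients".
- **Respiratory status.** The cohort has a lower bound, "Requiring supplementary oxygen" (8.4.1), and an upper bound that excludes patients "Requiring a high flow cannula, any ventilation or ECMO during first 24 hours post baseline" (8.4.2).
- **Propensity score (8.7).** Nine items: month, centre tier, sex, age, ethnicity, clinically extremely vulnerable status, comorbidities, place of acquisition, and HDU/ICU admission at baseline.
- **Balance (8.7).** A risk score for the primary outcome is fitted in all eligible non-RDV patients, and "the following key risk factors will be fitted as covariates: sex, age, and number of comorbidities". If the absolute standardised difference (ASD) of that score is below 0.1, "the matching will be considered balanced". The propensity model is revised only if balance is judged to have failed.
- **Primary model (17.2.1).** Logistic regression on treatment, ideally adjusted for age, sex and number of comorbidities.
- **Collected but not used above.** "Number of days since onset of symptoms" is a descriptive baseline variable (17.1). SpO2, FiO2 and oxygen flow appear as CRF fields in Appendix Table 1.
- **Severity elsewhere.** Day-15 clinical status (17.2.2.4) is analysed with a "proportional odds model with treatment arm and disease severity as covariates". Disease severity is not defined there and is named in no other model.

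**The concern.** In an observational comparison of a drug given at the clinician's discretion, the main threat is confounding by indication. The SAP itself identifies symptom duration as a condition of recommended use, so it plausibly drives treatment, and it marks the stage of illness. Oxygen requirement on the first day plausibly drives both the decision to treat and the risk of death. If neither enters the matching, RDV patients and controls may differ in both. If the pass rule does not contain them, the analyst can follow the plan correctly, declare balance, and report a 14-day mortality odds ratio that partly reflects who was chosen for treatment. Controls beyond the 10-day limit would also sit in a cohort described as eligible for RDV.

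**Working it through.** **1. Where each variable enters.**

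| Variable | Cohort (8.4) | Propensity score (8.7) | Risk score (8.7) | Primary model (17.2.1) | Collected |
|---|---|---|---|---|---|
| Age | 18 or over | yes | yes | yes | yes |
| Sex | no | yes | yes | yes | yes |
| Comorbidities | chronic kidney disease excluded | yes (six conditions) | count | count | yes |
| Month, tier, ethnicity, HDU/ICU | no | yes | no | no | yes |
| Days since onset | no | no | no | no | yes (17.1) |
| SpO2, FiO2, oxygen flow | band only | no | no | no | yes (Appendix) |

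The timing criteria in 8.4 run from baseline to RDV initiation, not from symptom onset. The SAP does take control eligibility seriously elsewhere: footnote a to 8.4.1 drops ages 12 to 17 so that no control is likely to fall below the weight limit. A patient without a Day 1 Daily Treatment CRF is excluded (8.4.2), so that form exists for every cohort member, although its oxygen fields may be incomplete.

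**2. The plan's own figures reproduce.** SAP 17.2.1 takes 14-day mortality of 3.1% in 500 RDV patients: 500 × 0.031 = 15.5, rounded to 16 deaths; 2 × 16 = 32 under 1:1 matching. These are not in dispute.

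**3. Illustrative bias from one omitted binary marker (assumed inputs).** Let the marker (high oxygen need) have prevalence p_T in RDV patients and p_C in controls after matching, let it carry odds ratio ψ for death, and let the true RDV odds ratio be 1. Group mortality is m = p·r1 + (1 − p)·r0, where r1 and r0 are the risks with and without the marker and r1/(1 − r1) = ψ·r0/(1 − r0). Control mortality is fixed at 3.1%.

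Example with p_T = 0.5, p_C = 0.3, ψ = 3: r0 = 0.0198 and r1 = 0.0571.
- m_C = 0.3 × 0.0571 + 0.7 × 0.0198 = 0.0310
- m_T = 0.5 × 0.0571 + 0.5 × 0.0198 = 0.0385
- Apparent OR = (0.0385/0.9615) / (0.0310/0.9690) = 1.25

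| p_T vs p_C | ψ = 2 | ψ = 3 | ψ = 4 |
|---|---|---|---|
| 0.4 vs 0.3 | 1.08 | 1.12 | 1.16 |
| 0.5 vs 0.3 | 1.15 | 1.25 | 1.32 |
| 0.3 vs 0.4 | 0.93 | 0.89 | 0.86 |
| 0.3 vs 0.5 | 0.87 | 0.80 | 0.76 |

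For ψ of 2 and 3 the results are almost the same at mortality of 10% or 20%.

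The marker's own ASD is |p_T − p_C| / √{[p_T(1 − p_T) + p_C(1 − p_C)]/2}:
- 0.4 vs 0.3: 0.10/√0.225 = 0.21
- 0.5 vs 0.3: 0.20/√0.230 = 0.42

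Both exceed 0.1.

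**4. Would the planned rule notice?** 300 cohorts of 500 RDV patients and 2,000 controls were simulated, standing for a matched cohort already balanced on age, sex and comorbidity count. Assumed: severity marker 30% vs 50% with mortality OR 3; more than 10 days of symptoms 5% vs 25%, with no effect on death; both independent of age, sex and comorbidities; true RDV OR 1; overall mortality about 10%. The risk-score ASD was below 0.1 in 96% of cohorts. In those cohorts the mean ASD was 0.42 for severity and 0.59 for long symptom duration, and the RDV OR adjusted for the three planned confounders averaged about 0.79.

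**The case against.** **Severity is not ignored.** A reader might infer that the plan omits respiratory severity altogether. It does not. The entry criteria hold the cohort between an oxygen requirement and the exclusion of high flow, ventilation and ECMO, and HDU/ICU admission is a propensity item. What remains is variation within that band.

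**Imbalance would not be wholly hidden.** SAP 17.1 tabulates baseline variables by group in the matched cohort, including days since onset, ethnicity and HDU/ICU. That stands, but no threshold attaches to the table and nothing in it triggers action. SpO2, FiO2 and oxygen flow are not on the 17.1 list. Month, tier, ethnicity and HDU/ICU are matched through the propensity score with a calliper, so for them the gap is a missing check, not a missing covariate.

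**The short risk-score list has a stated reason.** SAP 8.7 chose the most measurable factors, and SAP 18 warns that a propensity score needs complete data. This is a fair reason for a short risk score. It does not explain leaving days since onset out of the propensity model, nor the lack of covariate-level checks.

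**The plan admits its limits.** SAP 7 calls the analysis an ideal case open to documented adaptation, and SAP 11 accepts that isolated efficacy is hard to measure. Neither supplies the missing covariates.

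**The assumed bias is within the random error.** With 16 deaths in each group of 500, the 95% limits lie a factor of exp(1.96 × √(1/16 + 1/484 + 1/16 + 1/484)) = 2.0 either side of the OR. At 1:4 with equal risk (64 deaths in 2,000 controls) the factor is exp(1.96 × √(1/16 + 1/484 + 1/64 + 1/1936)) = 1.7. True, but imprecision does not remove bias, and the sample has no upper limit.

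**Conclusion.** The point holds in three parts. First, 8.2 and 8.4 do not agree on symptom duration, and that variable appears in no stage of the primary analysis. Second, oxygen need within the restricted band is neither matched on nor adjusted for in the primary analysis, although the plan names disease severity as a covariate for a secondary outcome. Third, the sole balance rule repeats the three variables the primary model adjusts for, so it cannot prompt a revision for imbalance in anything unrelated to them. These follow from the text alone and bear on the primary comparison.

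The size of the bias does not follow from the text. An apparent OR of 1.08 to 1.32 under a true null, or 0.93 to 0.76 in reverse, rests wholly on assumed prevalences and odds ratios, on the imbalance surviving the matching, and, for the rule's failure to notice, on independence from age, sex and comorbidity count. A reader might take these as an estimate for this study; the document gives no figure for oxygen need in either group, and even the direction is unknown.

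Nor do the documents settle that the 10-day limit must be imposed on the cohort. SAP 15 plans to count patients who received RDV outside guidelines, and SAP 11 sets out to evaluate RDV as used. They show only that the sections must be brought into line.

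**What to change.** 1. Reconcile 8.2 with 8.4, 8.4.1 and 8.4.2: state how symptom duration enters the cohort definition, for RDV patients and controls alike, and align the description of the cohort with the choice made.
2. Add days since symptom onset and a Day 1 oxygen measure (SpO2, FiO2 or flow) to the propensity model. RDV may begin at any time in the first 24 hours, so use pre-RDV values where timing allows. State how missing values are handled.
3. Declare the match balanced only if every propensity covariate, including the two new ones, has ASD below 0.1, and keep the risk-score ASD as a further condition.

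The cost is SAP wording and analyst time, with data already collected. Some patients with no onset date or Day 1 oxygen value will be lost or need imputation, and the completeness of those fields is unknown. The additions go into the propensity model, so they use none of the 10-events-per-covariate allowance that 17.2.1 sets for the mortality model. A stricter balance rule may require more than one revision of the propensity model.
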